6.3.4.2. Open-label Extension Period

For subjects randomized to mitapivat, the baseline for all assessments will be that derived in the Double-blind Period (Section 6.3.4.1).

For subjects randomized to placebo, the baseline is derived following the same rules as for the Double-blind Period but using start of mitapivat in the OLE Period instead of randomization date or 'reference date'.

Age at baseline will be calculated based on the date of informed consent for the study as described in Section 6.4.2.

6.3.5. On-Treatment Period

The on-treatment period starts on the date of the start of study treatment and ends 28 days after the end of study treatment (including dose taper period).

Within the on-treatment period, there are two distinct treatment periods:

- Double-blind on-treatment period starts on the date of the start of study treatment and ends
 - 28 days after the end of study treatment, for subjects who discontinue study treatment during the Double-blind Period of the study
 - Before the start of the OLE treatment period, for subjects who continue onto the OLE Period of the study

• OLE on-treatment period applies only to subjects who complete the Doubleblind Period of the study, and starts with the first dose of open-label mitapivat in the OLE Period and ends 28 days after the end of study treatment.

For subjects who receive mitapivat in the OLE Period, assessments or events occurring on the date of first dose of mitapivat in the OLE Period will be included in the analysis of the data from the double-blind on-treatment period, except for AEs and concomitant medications reported for subjects in the placebo arm which will be included only in the analysis of the data from the OLE on-treatment period.

Data listings will include all assessments and events, with those that occur outside of the on-treatment period flagged.

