²⁴Blood samples for pharmacokinetic and pharmacodynamic analysis will be collected at Week 12 (≤60 min predose) and Week 24 (≤60 min predose). If an RBC transfusion takes place during this visit, the blood samples for pharmacokinetic and pharmacodynamic analysis should be collected before the RBC transfusion.

²⁵Blood samples for pharmacokinetic and pharmacodynamic analysis will be collected at Week 36 (≤60 min predose, and 0.5 hr [±5 min], 1 hr [±5 min], 3 hr [±15 min], 5 hr [±15 min], and 7 hr [±30 min] postdose). If an RBC transfusion takes place during this visit, the blood samples for pharmacokinetic and pharmacodynamic analysis should be collected before the RBC transfusion.

²⁸ Study drug will be dispensed at every visit. Subjects must return study drug bottles (including empty bottles) and unused tablets at each visit to the clinical study center. The morning dose of study drug will be administered at the clinical study center during in-person visits to the clinical study center. During the Double-blind Period, subjects will be asked to record study drug dosing in a diary. The last dose of blinded study drug will be administered on the morning of the Week 48 visit. The first dose of open-label mitapivat will be administered on the evening of the Week 48 visit.

²⁹ Adverse events and SAEs will be collected throughout the study.

³⁰Concomitant medications, procedures, and surgeries are defined as all medications administered and procedures conducted from the first dose of study drug through 4 weeks after administration of the last dose of study drug (ie, EOS visit).

³¹ During the study, the subject's RBC transfusion schedule will be modified according to the guidance in Section 8.7. Information to be recorded for each transfusion is also in this section.

							O	pen-lab	el Exte	ension 1	Period	l						Safety Follow- up ²
Study Visit Week:	120	132	144	156 ³	168	180 ³	192	204 ³	216	228 ³	240	252 ³	264	276 ³	288	300 ³	312 ⁴	28 Days
Study Visit Day:	841	925	1,009	1,093	1,177	1,261	1,345	1,429	1,513	1,597	1,681	1,765	1,849	1,933	2,017	2,101	2,185	After Last Dose/ EOS
Study Visit Window (Days):	±14	±14	±14	±14	±14	±14	±14	±14	±14	±14	±14	±14	±14	±14	±14	±14	±14	+4
Procedures:																		
Pregnancy testing (WOCBP only) ⁵																		Х
BMD by DXA scan ⁶			Х				Х				Х				Х			
Physical examination																	Х	Х
Vital signs and weight ⁸	Х	Х	Х		X		Х		Х		Х		Х		Х		Х	Х
Hematology ⁹	Х	Х	Х		X		Х		Х		Х		Х		Х		Х	Х

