Clinical chemistry ¹⁰	Х	Х	Х		X		Х		Х		Х		Х		Х		Х	Х
Liver tests	Х	Х	Х		Х		Х		Х		Х		Х		Х		Х	Х
Lipid panel ¹²			Х				Х				Х				Х		Х	Х
Sex hormones ¹³	Х		Х		Х		Х		Х		Х		Х		Х		Х	Х
Iron panel ¹⁴	Х		Х		X		Х		Х		Х		Х		Х		Х	

Table 2: Schedule of Assessments (Continued)

		Open-label Extension Period ¹											Safety Follow- up ²					
Study Visit Week:	120	132	144	156 ³	168	180 ³	192	204 ³	216	228 ³	240	252 ³	264	276 ³	288	300 ³	312 ⁴	28 Day
Study Visit Day:	841	925	1,009	1,093	1,177	1,261	1,345	1,429	1,513	1,597	1,681	1,765	1,849	1,933	2,017	2,101	2,185	After Last Dose/ EOS
Study Visit Window (Days):	±14	±14	±14	±14	±14	±14	±14	±14	±14	±14	±14	±14	±14	±14	±14	±14	±14	+4
Procedures:																		
Study drug administration ¹⁷								Х (со	ontinuou	ıs)							X	
AEs and SAEs ¹⁸								Х	(conti	nuous)								X
Concomitant medications, procedures, and surgeries ¹⁹		X (continuous)										X						
On-treatment transfusion record ²⁰		X (continuous)																
Abbreviations: $AE =$ adverse even urea nitrogen; $CO_2 =$ carbon dioxie HCT = hematocrit; H lipoprotein cholesterol; MCH = m variation; SAE = serious adverse e Notes:	de; DX IDL-C ean co	A = c = high	lual-ener h-density	gy x-ray / lipopro	y absorp otein cho	tiometry olesterol	y; ;	cular hei	noglobi	n concer red bloc	ntration; od cell; l	E MCV = RDW-C	OS = En mean c V = red	nd of St corpuscu cell dist	udy; Hb llar volu tribution = wome	= hemog ; LDL-C me; width co	globin; = low-d oefficient dbearing	ensity t of potential.

Table 2. Schedule of Assessments (Continued)

At any time during the study, subjects who discontinue study drug should undergo the recommended dose taper and complete the assessments at the Safety Follow-up visit after administration of their last dose of study drug (ie, including the recommended dose taper). Subjects who withdraw from the study should be encouraged to first undergo the recommended dose taper (Table 4) and complete the Safety Follow-up visit. Subjects who are discontinuing study drug should be monitored for signs of hemolysis and worsening of anemia, as clinically indicated. ² The Safety Follow-up visit is to be completed after administration of the last of any dose of study drug (ie, including the recommended dose taper).

AG348-C-018

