9.2. Procedures for Recording Adverse Events and Serious Adverse Events

9.2.1. Recording Adverse Events

Adverse events and SAEs that occur from the time of providing informed consent until 28 days after the administration of the last dose of study drug will be recorded on the appropriate pages of the eCRF.

Adverse events spontaneously reported by the subject and/or in response to open nonleading questions (eg, "How are you feeling?") from study personnel or revealed by observation, physical examination, or other diagnostic procedures will be collected at every visit and recorded in the subject's medical record and in the appropriate pages of the eCRF.

Adverse events will be followed until 28 days after administration of the last dose of study drug or until study termination. Subjects will be assessed at the Safety Follow-up visit to determine if any new AEs have occurred. Adverse events that are ongoing at the time of study drug discontinuation should be followed through the Safety Follow-up visit. After this period, Investigators should report only SAEs that are considered related to study drug. Subjects who are withdrawn from the study due to a study drug related SAE will continue to be followed until the SAE resolves or is declared chronic by the Investigator, or until the subject is lost to follow-up.

Any clinically significant deterioration in clinical laboratory assessments (see Section 9.1.3) or other clinical finding that is considered an AE must be recorded in the eCRF. When possible, signs and symptoms indicating a common underlying pathology should be noted as one comprehensive event.

Information to be reported in the description of each AE includes:

- A medical diagnosis of the event (if a medical diagnosis cannot be determined, a description of each sign or symptom characterizing the event should be recorded)
- Event onset date
- Event resolution date
- Whether the event is serious (Section 9.1.2)
- Severity of the event (Section 9.2.2)
- Relationship of the event to study drug (Section 9.2.3)
- Action taken with study drug
- Event outcome

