10.4.1.2. On-Treatment Period

The on-treatment period begins on the date of the start of study drug and ends 28 days after the end of study drug administration (including the recommended dose taper).

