7.7. Safety Analyses

Safety data from the double-blind on-treatment period (Section 6.3.5) will be summarized based on the safety analysis set, by treatment arm.

Safety data from the OLE on-treatment period alone (Section 6.3.5) will be summarized separately based on the OLE analysis set, by treatment arm and overall.

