7.7.3. Clinical Laboratory Data

Clinical laboratory test results will be expressed in SI units. For chemistry and hematology laboratory tests, the actual values and the changes from baseline will be summarized by study visit.

For each laboratory test performed in the study, a by-subject listing of laboratory test results will be presented with the corresponding CTCAE grades (if applicable), laboratory normal ranges, and flags for values below lower limit of normal (LLN) or above upper limit of normal (ULN).

Parameters with CTCAE grades available:

Clinical laboratory test results will be graded according to CTCAE v4.03 as applicable. Grading will be derived based on the numerical thresholds defined by the CTCAE criteria. Non-numerical qualifiers will not be taken into consideration in the derivation of CTCAE grading.

Laboratory test results classified according to CTCAE will be described using the worst grade. For parameters graded with 2 separate toxicity criteria, such as potassium (hypokalemia/hyperkalemia), the toxicities will be summarized separately. Low direction toxicity (eg, hypokalemia) grades at baseline and postbaseline will be set to 0 when the variables are derived for summarizing high direction toxicity (eg, hyperkalemia), and vice versa.

The frequency of subjects with laboratory toxicities during the on-treatment period will be tabulated as follows. The denominator used to calculate percentages for each laboratory test is the number of subjects evaluable for CTCAE grading for that parameter (ie, those subjects for whom a Grade of 0, 1, 2, 3 or 4 can be derived).

• The summary of laboratory parameters by CTCAE grade will include the number and percentage of subjects with Grade 1, 2, 3, 4; Grade 3-4; and Any Grade (Grades 1-4) during the on-treatment period. The highest CTCAE grade during the on-treatment period is considered the worst grade.

- The shift table will summarize baseline CTCAE grade versus worst CTCAE grade during the on-treatment period. The highest CTCAE grade during the on-treatment period is considered the worst grade.
- Newly occurring or worsening laboratory abnormalities (Any Grade, Grade 3-4) during the on-treatment period will also be summarized.

Parameters with CTCAE grades not available:

Results of laboratory tests that are not part of CTCAE will be presented according to the following categories: below the LLN, within normal limits, and above the ULN according to the laboratory normal ranges.

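### Laboratory, vital-sign and weight results from a compliant Safety Follow-up visit on days 29 to 32 after the last dose fall outside the on-treatment period and so out of the safety summaries

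*SAP*

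**What the plan says.** **Visit timing.** The last column of Protocol Table 2 (section 1.2) is the Safety Follow-up visit, set at 28 days and headed "After Last Dose/ EOS". Its window is printed as +4, while the other columns in that row carry ±14. A table footnote fixes the anchor: "The Safety Follow-up visit is to be completed after administration of the last of any dose of study drug (ie, including the recommended dose taper"). The visit includes hematology, chemistry, liver tests, lipids, sex hormones, vital signs and weight.

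**On-treatment period.** Protocol 10.4.1.2 says the period "ends 28 days after the end of study drug administration (including the recommended dose taper"). SAP 6.3.5 gives the same 28 days and also includes the taper: "The on-treatment period starts on the date of the start of study treatment and ends 28 days after the end of study treatment". Neither text allows for the visit window.

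**What is summarized.** SAP 7.7: "Safety data from the double-blind on-treatment period (Section 6.3.5) will be summarized based on the safety analysis set, by treatment arm". For the extension: "Safety data from the OLE on-treatment period alone (Section 6.3.5) will be summarized separately based on the OLE analysis set". SAP 7.7.3 repeats the limit for graded tests: "The frequency of subjects with laboratory toxicities during the on-treatment period will be tabulated as follows". SAP 7.7.3.2 and 7.7.3.3 repeat it for liver-test categories and sex-hormone shifts. Under SAP 6.3.5, results outside the period are listed with a flag.

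**Adverse events.** SAP 7.7.1 classifies them by onset date. Protocol 9.2.1 records them "until 28 days after the administration of the last dose of study drug", and also has subjects assessed for new events at the Safety Follow-up visit.

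**The concern.** The visit and the analysis cut-off share a target day and an anchor, but only the visit has a tolerance, and it runs in one direction: later. A site that follows the schedule exactly can produce a safety panel that the analysis rule then excludes.

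This looks unintended. The schedule's footnote on concomitant therapy treats the 4-week point and the end-of-study visit as the same thing. SAP section 2 runs the double-blind data cut to the end of safety follow-up for subjects who stop treatment, so the results are in the primary report's data but not in its tables. Deaths after the period have their own category in SAP 7.7.2; laboratory and vital-sign results have none.

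At stake is the scheduled assessment after study drug stops. In the double-blind comparison the people concerned are treatment discontinuers, whose safety results are of particular interest. The protocol repeatedly asks for monitoring for hemolysis and worsening anemia after stopping. Whether a discontinuer's post-drug panel is tabulated can turn on one day of scheduling.

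**Working it through.** The documents state no figure on this point to reproduce. The check is a day count followed by a search for any rule that would bring the results back.

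**Inputs**
- Visit target: day 28 after the last dose; window +4 (Protocol Table 2).
- Cut-off: day 28 after the last dose (Protocol 10.4.1.2; SAP 6.3.5).
- Anchor: last dose including taper, for both. SAP 6.3.2 ends treatment at the latest non-zero dose, which agrees.

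**Day count**
- Permitted visit days: 28 to 28 + 4 = 28, 29, 30, 31, 32, which is 5 days.
- On or before the cut-off: day 28, which is 1 day.
- After the cut-off: days 29 to 32, which is 5 − 1 = 4 days. Share of permitted days excluded: 4/5.

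**Sensitivity to reading**
- SAP 6.4.2 counts durations as date − reference + 1. If the cut-off were counted that way, it would fall 27 days after the last dose and all 5 permitted days would be outside. The 4-of-5 count is the reading kinder to the plan.
- If the window were ±4 instead of the printed +4, permitted days would be 24 to 32 (9 days), with 4 of 9 outside. The mismatch would remain.

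**Is there a rescuing rule?**
- SAP 6.4.5 defines analysis visit windows for iron metabolism and bone mineral density, and mentions transfusion burden. It does not cover safety laboratory tests or vital signs.
- SAP 6.4.5 uses scheduled visits for by-visit descriptive statistics and admits unscheduled results to worst-value summaries. The latter are still confined to the on-treatment period.
- For worst-grade, shift and liver-test tables, the limit is written into their own sections. For by-visit laboratory and vital-sign tables (SAP 7.7.3, 7.7.4), it comes from the lead sentences of SAP 7.7. Protocol 10.4.4 describes by-visit summaries without that limit, but SAP 7.7 adds it.
- No other SAP rule readmits a day 29 to 32 result.

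**Who is affected**
- Double-blind: subjects who stop treatment and attend after day 28. Those who roll over are unaffected at Week 48, because their double-blind period ends when the extension begins.
- Extension: subjects, whether completing or stopping early, whose final visit falls after day 28.

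**Effect of the fix.** With results from the in-window visit included up to day 32, excluded permitted days fall from 4 of 5 to 0 of 5.

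**The case against.** The best defence is that 28 days is a sound exposure definition. Protocol 2.1.2.1 gives a longest mean terminal half-life of 79.3 hours and an effective half-life of about 3 to 6 hours. Twenty-eight days is 28 × 24 = 672 hours, and 672/79.3 is about 8.5 of the longest half-lives. The first 28 days after stopping, when acute effects would be expected, are wholly inside the period, and unscheduled results from those days enter the worst-value summaries. Nothing is lost, since later results are listed and flagged. No efficacy endpoint or hypothesis test is touched.

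This supports keeping day 28 for adverse events. It does not explain why a scheduled visit, done within its permitted window, should be left out of the tables.

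The defence also disposes of several stronger readings:
- **A reader might infer that all safety information from a late visit disappears.** It does not. An event with onset by day 28 that is first reported on day 32 remains treatment-emergent.
- **A reader might infer that a new abnormality found at the visit goes unrecorded.** Protocol 9.2.1 looks for new events at that visit, Table 2 carries adverse event collection through it, and 9.3.1 requires related serious events to be reported after day 28. The texts are inconsistent; they do not show non-recording.
- **A reader might turn 4 of 5 days into 80% of panels**, then assume 5% to 15% discontinuation (12 to 36 of 240) and multiply by 0.8 to get about 10 to 29 subjects. That requires visits spread evenly over the window, although day 28 is the target. It also requires every discontinuer to attend, although Protocol 7.2 stops evaluations once consent is withdrawn. The documents give neither a visit distribution nor a discontinuation rate.
- **A reader might infer that every final visit in the extension is excluded.** A day 28 visit is included.

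**Conclusion.** The mismatch holds, within limits. On 4 of the 5 permitted days, laboratory, vital-sign and weight results from a compliant Safety Follow-up visit are excluded from the by-visit, worst-grade, shift and liver-test summaries and appear only in flagged listings. The day count rests on the printed +4 window and the shared taper-inclusive anchor, and needs no further assumption. The number of subjects affected cannot be derived. The consequence is confined to descriptive safety tables: for the primary report, treatment discontinuers seen after day 28; for the extension addendum, subjects whose final visit falls after day 28. It is worth settling before database lock, because otherwise the treatment of an in-window panel depends on its calendar date.

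**What to change.** **SAP (6.3.5 and 7.7).** State that laboratory, vital-sign and weight results from the scheduled Safety Follow-up visit, done within its protocol window (up to 32 days after the last dose), are included in the on-treatment summaries for both the double-blind and extension periods. Leave the 28-day window for treatment-emergent events as it is. Moving the whole cut-off to the later of day 28 and the visit date would be worse, because each subject's adverse event risk window would then depend on scheduling.

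**Protocol (9.2.1), separately.** Reconcile the day-28 end of adverse event recording with the statement that new events are assessed at the Safety Follow-up visit, and check 9.3.1 for consistency.

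**Cost.** The SAP change is about one sentence, with no new visit or test. SAP section 2 allows the SAP to modify protocol plans, and the primary endpoint is untouched. The downside is that a few tabulated results will date from up to 4 days beyond the 28-day period, under the same rule in both arms. The protocol wording would need an amendment with ethics approval under Protocol 11.1, so it should not hold up the SAP change.

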8.7. Red Blood Cell Transfusions and Transfusion Modifications

The first dose of study drug must be administered within 7 days after Transfusion 0. Transfusion 0 is defined as the last RBC transfusion that was administered before randomization. Randomization must not occur until T0 has been completed.

All blood samples must be collected before administration of the study drug and before an RBC transfusion, including Transfusion 0, if an RBC transfusion is scheduled on the same day.

Transfusion history will be recorded for the 24-week period before randomization. Transfusion history includes T0. On-treatment transfusions will also be recorded. The transfusion history and on-treatment transfusion record includes transfusion dates, number of RBC units transfused, and pretransfusion Hb concentration. An RBC unit refers to packed red blood cell (pRBC) preparations. Due to hematocrit concentration differences in blood products used per local standards of care, 2 units of whole blood are equivalent to 1 unit of pRBCs and constitute an RBC unit. If available, the volume and the hematocrit of each transfused RBC unit should also be recorded. All RBC transfusions, including those received outside of the clinical study center, must be recorded.

A pretransfusion Hb threshold will be determined for each subject based on transfusion history. The pretransfusion Hb threshold is defined as the mean of all documented pretransfusion Hb concentration values recorded for the RBC transfusions administered during the 24-week transfusion history.

During the study, Investigators will monitor changes in Hb concentration and modify the subject's RBC transfusion schedule according to the guidelines in Table 10. Study drug dose modification guidance for excessive Hb response is provided in Section 6.7.1.1.

Subjects may receive RBC transfusions at the discretion of the Investigator for acute symptoms related to anemia or other comorbidities requiring immediate treatment (eg, infection or cardiopulmonary compromise).

Pretransfusion Hb Concentration ¹	RBC Transfusion Modification	
Hb concentration ≥ 1 g/dL above the pretransfusion Hb threshold and \leq ULN (by sex)	Delay RBC transfusion or decrease the number of RBC units to be transfused.	
>ULN (by sex)	Delay RBC transfusion.	
	• Recheck Hb concentration within 28 days.	
	• If Hb concentration remains >ULN (by sex) for ≥4 weeks, in the absence of RBC transfusions, modify the study drug dose as described in Section 6.7.1.1.	

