6.3.2. Start and End Dates of Study Treatment

The start of study treatment is the earliest date/time of administration of a non-zero dose of the study drug.

The end of study treatment is the latest date/time of administration of a non-zero dose of the study drug on or before the EODB period date/ EOS date.

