6.3.4. Baseline

6.3.4.1. Double-blind Period

Throughout the SAP for analyses based on the Double-blind Period, 'reference date' will be used to refer to randomization date for subjects randomized and not dosed, or the start of study treatment for subjects randomized and dosed.

Efficacy Evaluations

The 24-week baseline transfusion burden is defined as the total number of RBC units transfused during the 24-week period (168 days) before the 'reference date'. Baseline transfusion burden will be standardized to match the postbaseline assessment duration specified for each endpoint associated with reduction of transfusion burden from baseline.

For iron metabolism (Section 7.6.3.2),

baseline is defined as the last assessment before Transfusion 0 (the last RBC transfusion that is administered before randomization) to minimize the impact of transfusion on these endpoints. Baseline will be derived based on central laboratory data; if no central laboratory data are available, then local laboratory data will be used to derive the baseline.

Demographic and Other Baseline Characteristics

For summaries of demographic and other baseline characteristics based on the FAS, baseline is defined as the last assessment before the 'reference date'.

Safety Evaluations

For clinical laboratory assessments the following applies:

• Before deriving the baseline:

- If there are multiple records with the same assessment day and time from the same laboratory, the average value will be used.
- If there are multiple records with the same assessment day and time from different laboratories, the value from the central laboratory will be used.
- The baseline will then be the last value before the start of study treatment.

For all other safety parameters, the last assessment before the start of study treatment will be used as the baseline.

PD Evaluations

The baseline is defined as the pre-dose whole blood concentration of 2,3-DPG and ATP on study day 1. If this concentration is <LLQ, baseline will be set to missing.

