7.7.3.2. Chemistry

Liver function tests: Alanine aminotransferase (ALT), aspartate aminotransferase (AST), alkaline phosphatase (ALP), and total bilirubin are used to assess possible drug-induced liver toxicity. The ratios of test result to ULN will be calculated and categorized for these parameters during the on-treatment period.

The summary of liver function tests will include the following categories. The frequency of subjects with each of the following during the on-treatment period will be summarized by treatment arm:

- ALT >3×ULN, ALT >5×ULN, ALT >10×ULN, ALT >20×ULN
- AST >3×ULN, AST >5×ULN, AST >10×ULN, AST >20×ULN
- (ALT or AST) >3×ULN, (ALT or AST) >5×ULN, (ALT or AST) >10×ULN, (ALT or AST) >20×ULN
- total bilirubin >2×ULN
- Concurrent ALT >3×ULN and total bilirubin >2×ULN
- Concurrent AST >3×ULN and total bilirubin >2×ULN
- Concurrent (ALT or AST) >3×ULN and total bilirubin >2×ULN
- Concurrent (ALT or AST) >3×ULN and total bilirubin >2×ULN and ALP ≥2×ULN
- Concurrent (ALT or AST) >3×ULN and total bilirubin >2×ULN and (ALP <2×ULN or missing)

Concurrent measurements are those occurring on the same date.

Categories will be cumulative, ie, a subject with an AST $>10\times$ ULN will also appear in the categories $>5\times$ ULN and $>3\times$ ULN. Liver function test elevation and possible Hy's Law cases will be summarized using frequency counts and percentages.

An evaluation of Drug-Induced Serious Hepatotoxicity (eDISH) plot will be created, with different symbols for different treatment arms, by graphically displaying:

- Peak serum ALT (/ULN) vs peak total bilirubin (/ULN) including reference lines at ALT=3×ULN and total bilirubin=2×ULN
- Peak serum AST (/ULN) vs peak total bilirubin (/ULN) including reference lines at AST=3×ULN and total bilirubin=2×ULN

For **calcium**, CTCAE grading is based on corrected calcium and ionized calcium. Corrected Calcium is calculated from albumin and calcium as follows:

Corrected calcium (mmol/L)=measured total calcium (mmol/L)+ $0.02 \times [40$ -serum albumin (g/L)]

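### The on-treatment period starts on the calendar date of first dose, so the pre-dose Day 1 laboratory sample is both the baseline and an on-treatment value in the worst-grade and liver-threshold tables

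*SAP*

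**What the plan says.** Both documents define the on-treatment period by calendar date. SAP 6.3.5: "The on-treatment period starts on the date of the start of study treatment and ends 28 days after the end of study treatment". Protocol 10.4.1.2: "The on-treatment period begins on the date of the start of study drug and ends 28 days after the end of study drug administration".

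Treatment start itself has finer resolution. SAP 6.3.2: "The start of study treatment is the earliest date/time of administration of a non-zero dose of the study drug". The laboratory safety baseline in SAP 6.3.4.1 is tied to that moment: "The baseline will then be the last value before the start of study treatment".

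Day 1 samples are pre-dose by design. Protocol 8.7: "All blood samples must be collected before administration of the study drug and before an RBC transfusion". SAP 6.3.4.1 also assumes that a scheduled Day 1 assessment with a missing time was taken before the dose. Table 1 of the protocol places hematology, clinical chemistry, liver tests, coagulation and sex hormones on Day 1.

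The affected outputs search the whole on-treatment period. SAP 7.7.3: "The shift table will summarize baseline CTCAE grade versus worst CTCAE grade during the on-treatment period". It takes the worst grade as the highest in that period. SAP 7.7.3.2, on the liver tests: "The ratios of test result to ULN will be calculated and categorized for these parameters during the on-treatment period". Neither section limits the search to values after dosing or after baseline.

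**The concern.** A date-based period and a baseline based on date and time overlap on Day 1. One pre-dose result can then serve on both sides of a comparison that is meant to contrast before with after.

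Two things are at stake in the safety report. First, the CTCAE shift table loses its ability to show improvement for tests with a Day 1 baseline. Second, counts presented as on-treatment abnormalities, including ALT or AST above 3×ULN, bilirubin above 2×ULN and concurrent elevations, take in subjects whose only abnormal sample preceded the first dose.

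Abnormal pre-dose liver tests are plausible here. Exclusion 8d allows AST and ALT above 2.5×ULN when attributed to hepatic iron (or, for AST, hemolysis), and the listed criteria set no numerical bilirubin limit. Improvement on drug is also plausible. In the sponsor's non-transfusion-dependent study (Protocol 2.1.2.3.2), mean indirect bilirubin was 31.49 µmol/L at baseline and changed by −17.72 µmol/L. That was an uncontrolled study in a different population, so it supports the direction only.

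**Working it through.** The plan gives no figure to reproduce on this point. The check is an enumeration, followed by a range under stated assumptions.

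**1. CTCAE worst-grade shift table.** Let b be the Day 1 baseline grade and w the worst grade after dosing, each 0 to 4, giving 5 × 5 = 25 pairs.
- As written: tabulated worst = max(b, w), which is never below b. Improvement cells reachable: 0 of 10. In the 10 pairs with w < b, the tabulated worst grade is too high.
- Post-dose values only: tabulated worst = w. Improvement cells reachable: 10 of 10.

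**2. New-or-worsening table.** A subject counts if the worst grade exceeds b. Now max(b, w) > b exactly when w > b, which is 10 of 25 pairs under both rules. This table does not change.

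**3. Tests without CTCAE grades, and sex hormones.** SAP 7.7.3 and 7.7.3.3 tabulate shifts to each category (below LLN, normal, above ULN), not to a worst category. I read this as one entry for every category a subject reaches. There are 7 non-empty sets of post-dose categories. For an abnormal baseline:
- The normal cell is filled in 4 of 7 sets under both rules, so improvement stays visible.
- The no-change cell is filled in 7 of 7 sets as written, against 4 of 7 with post-dose values only.

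**4. Any-grade count.** Overcount = P(b ≥ 1) × P(w = 0 given b ≥ 1), taking every subject to have at least one post-dose value. The documents give neither probability. Over assumed ranges, in percentage points:

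| Abnormal on Day 1 | 5% normalise | 15% normalise | 30% normalise |
|---|---|---|---|
| 10% | 0.5 | 1.5 | 3.0 |
| 30% | 1.5 | 4.5 | 9.0 |
| 50% | 2.5 | 7.5 | 15.0 |

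With the planned 160 and 80 subjects, the extremes are 160 × 0.005 = 0.8 and 80 × 0.005 = 0.4 subjects, up to 160 × 0.15 = 24 and 80 × 0.15 = 12. The liver-threshold counts follow the same formula, with being above the threshold in place of grade ≥ 1.

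**5. Arm comparison.** The difference between arms shifts by the mitapivat overcount minus the placebo overcount. With the same Day 1 prevalence, equal normalisation gives a shift of 0. If 30% normalise on mitapivat and 5% on placebo, the shift is 3.0 − 0.5 = 2.5 points at 10% prevalence and 15.0 − 2.5 = 12.5 points at 50%, against mitapivat in both cases.

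**6. Where there is no overlap.** DXA and the lipid panel have no Day 1 assessment in Table 1. For the open-label switch, SAP 6.3.5 has a same-date rule: assessments or events "occurring on the date of first dose of mitapivat in the OLE Period will be included in the analysis of the data" of the double-blind on-treatment period, with an exception only for adverse events and concomitant medications in the placebo arm.

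**The case against.** The best defence is that a competent programmer would drop the baseline record anyway. SAP 6.3.4.1 already sorts Day 1 records into pre-dose and post-dose, and SAP 7.7.3 speaks of grades at baseline and postbaseline as though they were separate. This stands only in part. The sorting rule serves the choice of baseline. The postbaseline wording belongs to the rule that sets opposite-direction toxicities to 0, and it does not limit the worst-grade search. The SAP deals with same-day records at the open-label switch, and it starts the visit windows in 6.4.5 on study day 2. It has no such rule for laboratory values on Day 1.

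The defence is right about scope. Only descriptive safety tables are involved, listings still show every value, and the table that displays deterioration is unchanged. Exclusion 8d also limits, without eliminating, pre-dose transaminase elevations.

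Three stronger readings are tempting, and the documents do not support them:
- A reader might infer that no shift table can show improvement. This holds only for the CTCAE worst-grade table (steps 1 and 3).
- A reader might infer that both arms are inflated equally and the comparison is therefore pulled toward no difference. Equal inflation leaves a difference unchanged. A shift needs unequal normalisation, for which the documents give no figure.
- A reader might infer that a coagulation table could hold only pre-dose values. That is true of scheduled samples, but SAP 6.4.5 admits unscheduled results to worst-value summaries, and 7.7.3 names no specific coagulation output.

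**Conclusion.** The concern holds for the CTCAE worst-grade shift table, the any-grade counts and the liver-threshold counts, for tests whose baseline is a Day 1 sample. The rule is stated, and followed literally it gives the wrong table. This is more than an unstated detail.

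The overcount is 0.5 to 15 percentage points for any-grade abnormality, on the assumption that 10–50% are abnormal on Day 1 and 5–30% of those are normal throughout afterwards. The distortion between arms is nil if normalisation is equal, and up to 12.5 points at the extremes of the same assumed ranges. In the non-CTCAE and sex-hormone shift tables the only effect is a no-change cell that is always filled. The new-or-worsening, DXA, lipid and open-label tables are unaffected, as are the efficacy analyses and type I error.

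The SAP should be corrected before unblinding, because liver-safety counts should not rest on an unwritten convention.

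**What to change.** In SAP 6.3.5 and 7.7.3, and in Protocol 10.4.1.2, add: *For laboratory, vital-sign and other assessments, on-treatment values are those obtained after the date and time of the first dose. Day 1 assessments classed as pre-dose under SAP 6.3.4.1, including the record used as baseline, are not on-treatment values.*

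Keep the date-based start for adverse events. Counting by date there may include an event that began shortly before the dose, but it does not miss events.

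Add a note that coagulation has no scheduled post-dose samples, so any on-treatment coagulation summary rests on unscheduled post-dose results, if there are any. Do not restrict coagulation to listings, since that could drop such results.

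The cost is this wording and one programming filter, with no new data. One consequence to expect is that a subject with no post-dose result for a test leaves that test's on-treatment denominator.
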